During brief clinical assessments, symptoms of depression, PTSD, and other clinical conditions common in this population, such as tinnitus, will be collected using brief self-report measures. Subjects will also respond to a clinician-administered PTSD scale and will be queried regarding adverse events. These follow-ups do not always require the subject to be physically present, and will often be carried out over the phone or Zoom video conferencing. At 1 and 2 month/s post completion of the final feedback session, subjects will undergo a full clinical assessment. Similar measures will be collected during these assessments, in addition to the Clinician Administered PTSD Scale for DSM-V (CAPS-5).

E. Genetic Testing

Adult PTSD patients will be asked via a separate consent form (see below for more details) to provide DNA and RNA samples. Both DNA and RNA will be collected in order to conduct sequencing of DNA and RNA. Analyses will focus on genes best supported by the PTSD literature at the time of analysis. Genetic data collected may be related to the imaging data to examine, for example, whether genetic markers are associated with learning over the course of the neurofeedback protocol. See below for more details on genetic testing. The genetic component of the present study will occur in collaboration with a pre-existing protocol that examines the genetics of neuropsychiatric disorders (HIC0301024156; "Genetic and molecular studies of developmental neuropsychiatric disorders associated with cognitive and behavioral impairment"). All participants who choose to provide DNA and RNA samples will be consented under this protocol, and all genetic data collected by these means will be shared with personnel associated with this protocol.

5. Genetic Testing (continued)

A. Describe

- i. the types of future research to be conducted using the materials, specifying if immortalization of cell lines, whole exome or genome sequencing, genome wide association studies, or animal studies are planned.

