This study will seek out subjects of all sexes, ages 18 and up. Inclusion criteria include an active and primary diagnosis of chronic PTSD, as established by the Clinician Administered PTSD Scale for DSM-V (CAPS-5). The subjects must be able to give signed, informed consent and follow instructions in English and have normal or corrected-to-normal vision. Subjects must be unmedicated or on a stable dose of SSRIs for 2 months prior to enrollment in the study, and must not have initiated cognitive-behavioral therapy or any other evidence-based therapy for PTSD within the past 3 months. What's more, subjects must have no intention of changing their medication or psychotherapy, or enrolling in another research study testing an experimental intervention, during the 2.5-month period of the intervention. However, if unforeseen changes in clinical condition occur during the study, we will not discourage subjects from withdrawing from the study to seek new treatments. Subjects with any primary psychiatric diagnosis of a current mood disorder, psychotic disorder, autism, mental retardation, or DSM-5 substance use disorder will be excluded from participation. Subjects with any history of psychosis or mania will also be excluded. While comorbid mood and anxiety disorders will be permitted if they are not the primary focus of clinical attention, active suicidality within the past year or a history of suicide attempt in the past 2 years will result in exclusion. As this study involves MRI, any subjects with contraindications to MR scanning (e.g., pregnancy, ferromagnetic metal in body, severe claustrophobia) will be unable to participate. Finally, any subjects with a history of unstable medical

or neurological condition, or history of brain surgery, epilepsy, or other brain injury will be excluded from participation.

7. **Subject Classification:** Check off all classifications of subjects that will be specifically recruited for enrollment in the research project. Will subjects who may require additional safeguards or other considerations be enrolled in the study? If so, identify the population of subjects requiring special safeguards and provide a justification for their involvement.

None of the populations listed below will be specifically recruited for enrollment.

 Children	 Healthy	 Fetal material, placenta, or dead fetus

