At every clinical assessment, including brief ones, we collect the Beck Depression Index (BDI; Beck et al. 1961), which monitors suicidality, as well as information regarding adverse events and worsening of symptoms. These assessments are scheduled to occur at approximately half week intervals during the active part of the intervention and at month intervals during follow-up. If any issues arise, [name] will be notified and will review the data. The guidelines of our IRB will be followed in the case of all adverse events. In the case of worsening symptoms or endorsement of suicidal ideation on the BDI (as indicated by a score of 2 or higher on question 9), [name] will arrange an in-person assessment of the participant. As required by law, if needed, [name] will admit the participant into Yale-New Haven hospital for further monitoring. In the case of difficult decisions, [name] will consult the Independent Monitoring Committee.

As mentioned above, the Independent Monitoring Committee consists of Drs. [name] and [name]. Every six months, the members of this committee will receive reports from the study team about the occurrence of adverse events, the progress of recruitment, the demographic characteristics of enrolled participants, the number of dropouts and participants' reasons for dropping out, as well as any protocol amendments. They will also be consulted if any difficult situations arise or if there are any serious and unanticipated adverse events that are possibly, probably, or definitely related to the study. These two committee members are extremely experienced in the assessment and the outpatient and inpatient management of all psychiatric emergencies, with particular expertise in PTSD and related disorders. They will be an ideal sounding-board and resource for the resolution of any challenging clinical situations that may arise during the conduct of this research. In the unlikely event that [name] and the committee members have differing opinions as to the appropriate clinical choice for a particular patient, decisions made by the committee will be determinative, on the presumption that their external perspective will most appropriately weight the patients' well-being.

3. Attribution of Adverse Events:

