- ii. *To determine if NF improves symptoms more than sham feedback and to correlate symptom changes with control over the amygdala:* A 2x2 ANOVA with factors group (2 levels: NF and sham) and time-point (2 levels: pre-intervention and first post-intervention) will be run on the past-month scores from the clinician-administered symptom checklist collected during the Full Clinical Assessment sessions. If there is a significant group-by-time-point interaction and post-hoc t-tests reveal a significantly greater improvement in symptoms in the NF group than the sham group, we will conclude the NF does improve clinical symptoms more than the sham. The change in score will also be correlated across NF subjects with the change in control over the brain area (computed as described above in section A.iv.). We hypothesize a decrease in score (indicating improvement in PTSD symptoms) will be correlated with an increase in control. A secondary analysis will be run using all 3 time points of scores collected (pre, 1 month post, and 2 month post intervention) to explore the long-term clinical effects. A linear mixed model analysis with group (NF or sham) by time-point (pre, 1 month post, and 2 month post intervention) will be used to capture the longitudinal effect of the clinical intervention. Finally, if the intervention does appear to reduce symptoms, we will explore whether these changes are greatest for scores on PTSD criterion B (intrusion) and criterion E (alteration in arousal reactivity) as these are expected to be most closely related to successful amygdala regulation.

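### The main symptom test drops any randomized subject without a 1-month score, and the plan neither follows subjects who withdraw nor says how missing scores are handled

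*Combined protocol and SAP*

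**What the plan says.** - **Withdrawal.** Section I.6 (Subject Population) says that if a subject's clinical condition changes unexpectedly, "we will not discourage subjects from withdrawing from the study to seek new treatments". The exit described is from the study, not only from the feedback sessions.
- **Main symptom test.** Section I.13.C.ii: "A 2x2 ANOVA with factors group (2 levels: NF and sham) and time-point (2 levels: pre-intervention and first post-intervention) will be run" on the past-month clinician-administered scores. The efficacy conclusion follows "If there is a significant group-by-time-point interaction and post-hoc t-tests reveal a significantly greater improvement in symptoms in the NF group" than in the sham group.
- **Timing of the post score.** Section I.4.D: "At 1 and 2 month/s post completion of the final feedback session, subjects will undergo a full clinical assessment", including the CAPS-5.
- **Secondary analysis.** Section I.13.C.ii also names a linear mixed model over pre, 1 month and 2 months, to explore longer-term effects. The conclusion does not depend on it.
- **Interim symptom scores.** Section I.4.D says of the brief assessments: "Subjects will also respond to a clinician-administered PTSD scale and will be queried regarding adverse events". Item 2 of the Data and Safety Monitoring Plan schedules clinical assessments at "approximately half week intervals during the active part of the intervention". Section I.4.C mentions only self-report checklists before in-magnet assessments. No analysis use is stated for any of these scores.
- **What is not stated.** The document gives no analysis set, missing-data method, sensitivity analysis, expected dropout rate or outcome collection after withdrawal. The number of dropouts and their reasons go to the monitoring committee every six months, with no link to the analysis.

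**The concern.** With two time points, a subject without the first-post score has no change score and cannot enter the interaction test or the t-test. The plan leaves room for subjects to leave the whole study because of their clinical course, which is what the post score measures. The subjects analysed would then be selected partly on outcome.

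At stake are the size and the credibility of the symptom comparison. Enrollment is 60 (Section III.1), and randomization comes only after the localizer (Section I.4.C.ii), so there are few subjects to lose.

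There are also plausible reasons for loss to differ by arm. If NF works, fewer NF subjects would have cause to leave. Subjects are told that the control is not believed to help (Section I.4.C.ii). Section III.6 promises disclosure of the assigned condition at study completion or termination, with NF then offered to sham subjects. A subject who is not improving may guess the assignment and have a motive to end early.

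**Working it through.** **1. Plan's own figure.** There is none to reproduce: no power statement, symptom effect size, SD or dropout rate.

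**2. Inputs.** From the document: 60 enrolled (Section III.1); NF count never below sham count (Section I.4.C.ii); two time points (Section I.13.C.ii). Assumed: 1:1 allocation and 30 per arm (the most that 60 can give at 1:1), two-sided alpha 0.05 (stated for the amygdala test only), SD of change = 1, and every withdrawal probability and symptom effect below.

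**3. Equivalence.** With two time points, the group-by-time F equals the square of the two-sample t on change scores. The test therefore uses complete pairs only.

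**4. Fewer subjects alone.** Power = Φ(d/√(2/n) − 1.96), with n per arm.

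| Loss | n per arm | Power, d = 0.5 | Power, d = 0.8 |
|---|---|---|---|
| 0% | 30 | 49% | 87% |
| 10% | 27 | 45% | 84% |
| 20% | 24 | 41% | 79% |
| 30% | 21 | 37% | 74% |

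**5. Loss related to outcome.** Let change X ~ N(μ, 1), positive = worse, with μ = 0 in sham and −D in NF. A subject with X > 0.5 withdraws with probability q. With a = 0.5 − μ and P = 1 − Φ(a):

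mean of completers = (μ − q[μP + φ(a)]) / (1 − qP)

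Worked case, D = 0.5 and q = 0.5 in both arms:
- Sham: P = 0.3085, φ(0.5) = 0.3521; mean = −0.1760/0.8457 = −0.208; loss 15%.
- NF: P = 0.1587, φ(1) = 0.2420; mean = (−0.5 − 0.5 × 0.1626)/0.9207 = −0.631; loss 8%.
- Difference = 0.631 − 0.208 = 0.423, against a true 0.50.

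Simulation of the same model (30 per arm, 4,000 replicates) agrees and gives rejection rates:

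| True D | q NF / sham | Loss NF / sham | Difference, formula (simulated) | Rejection |
|---|---|---|---|---|
| 0 | 0.25 to 0.8, same in both | 8–25% each | 0 (0.00 to −0.01) | 4.6–4.9% |
| 0.5 | 0 / 0 | 0 / 0 | 0.50 (0.49) | 47% |
| 0.5 | 0.25 / 0.25 | 4% / 8% | 0.47 (0.47) | 43% |
| 0.5 | 0.5 / 0.5 | 8% / 15% | 0.42 (0.43) | 37% |
| 0.5 | 0.8 / 0.8 | 13% / 24–25% | 0.35 (0.35) | 29% |
| 0 | 0.5 / 0 | 15–16% / 0 | +0.21 (+0.21) | 12% |
| 0 | 0 / 0.5 | 0 / 15–16% | −0.21 (−0.21) | 12% |
| 0 | 0.8 / 0.2 | 25% / 6% | +0.30 (+0.30) | 21% |
| 0 | 0.2 / 0.8 | 6% / 25% | −0.30 (−0.30) | 21% |

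**6. How much of the power loss is bias.** For D = 0.5 and q = 0.5, random loss of the same size leaves 30 × 0.921 = 27.6 and 30 × 0.846 = 25.4 subjects. Power is Φ(0.5/√(1/27.6 + 1/25.4) − 1.96) = Φ(−0.14) = 44%, down 5 points from 49%. The simulated fall is 10 points (47% to 37%), so about half comes from selection.

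A milder model makes withdrawal depend on worsening at a brief assessment, with 15–19% loss in NF and 19–26% in sham, correlations of 0.55–0.80, and effects in SD of the score. A true 0.50 is estimated at 0.44–0.49, and power falls from about 56% to 43–48%; random loss alone would give 49% to 46%. A true 0.70 is estimated at 0.63–0.69, and power falls from about 85% to 70–76%; random loss alone would give 77% to 74%. There, most of the fall is simply fewer subjects.

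**The case against.** The sentence in Section I.6 is a voluntariness statement. A reader might infer that the plan expects worsening subjects to leave. It does not say so: it permits withdrawal, gives no rate, and refers to unforeseen changes in condition, not to worsening. Worsening is an inference from the stated purpose of seeking new treatment. A reader might also infer that the plan declares a completers' analysis. It does not; that follows by default from a two-time-point test with no other rule. Both corrections stand, and freedom to withdraw is not the flaw.

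A stronger reading is that the randomized comparison is broken and false positives will follow. The calculations do not support this in general. With one withdrawal pattern in both arms and no true effect, type I error stays near 5%, and with a true effect the bias is conservative. A spurious benefit needs patterns that differ by arm, and subjects and post-randomization assessors are blind (Section I.4.C.ii). That limits the risk, though the incentives created by disclosure on termination mean it is not excluded.

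There are real mitigations: sessions about half a week apart, payment at each visit, exclusion of subjects who intend to change treatment, remote assessments, and reporting of dropouts to the monitoring committee. They may keep loss low. They do not say what happens to those who are lost.

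Finally, a mixed model is already planned. But it uses only pre, 1-month and 2-month scores, so a subject lost before 1 month contributes a baseline value and almost nothing to the group-by-time contrast. Nor should simulated recovery by imputation from brief scores be taken as proof of a cure: where withdrawal is generated from those scores, recovery is built in.

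**Conclusion.** The point holds as a gap in Section I.13.C.ii, made consequential by Section I.6. Subjects may leave the study when their condition changes, their outcomes are not then sought, and the test that decides the symptom question can use only those with a 1-month score.

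Under a common withdrawal pattern the consequence is lost power and bias towards the null, modest at moderate loss. Across the illustrations the shrinkage runs from 0.01 SD in the mild model to 0.15 SD at the harshest setting, for a true 0.50. If the pattern differs by arm, the direction is open.

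Neither size nor direction can be derived from the document. Dropout rates, effect sizes, correlations, 1:1 allocation and the 0.05 level for this test are all assumptions. This is a change that should be made because it is cheap and gives a better analysis, not because the trial is shown to be invalid.

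**What to change.** **Sections I.6 and I.4.D.** Distinguish stopping the intervention from stopping follow-up. With consent, and without limiting anyone's right to leave or to seek care, seek the 1- and 2-month CAPS-5 from everyone randomized, by phone or video where needed. The rater should still be blind, and the score should be obtained before any crossover to NF. The timing of disclosure in Section III.6 needs to be aligned with this.

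**Section I.13.C.ii.** Replace the ANOVA as the main symptom analysis with a likelihood-based mixed model:
- Include all randomized subjects by assigned arm, with the 1-month group contrast as the main estimate and the pre-intervention score in the model.
- Use the brief-assessment PTSD scores as repeated or auxiliary data, or in multiple imputation. Without them, the three-time-point model does little for subjects lost before 1 month.
- State which brief scores exist. The self-report checklists in Section I.4.C are clear; a half-weekly clinician rating is a fair but not certain reading of Section I.4.D together with the monitoring plan.
- Add one sensitivity analysis that assumes worse outcomes in those lost, and report withdrawals by arm and reason.

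**Cost.** Analysis-plan wording, a consent line and a few extra remote assessments. The model combines different PTSD instruments, which needs care. Scores obtained after withdrawal may reflect other treatments and must be interpreted as such.

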After the Initial Clinical Assessment, participants will meet in person or virtually with a clinician to take part in a strategy development session, the goal of which is to develop an individualized cognitive strategy for the subject that may provide them with some initial control over their amygdala activity. While strategies discussed during this session are intended to assist individuals in raising/lowering amygdala activity after trauma recall, they are meant only to engender an initial, limited ability to control the amygdala – a starting point for the feedback sessions. During the feedback sessions, subjects will have the chance to experiment with their cognitive strategies and receive direct feedback regarding what is more effective, thereby allowing subjects to develop increasing control over the amygdala in the way that best fits her/his individual style of coping. It is important to note that because this stage occurs before randomization, *all* subjects (NF and sham) participate in this session. Therefore, learning effects specific to the session are controlled for by group comparisons.

C. MR Imaging:

At this point, subjects are ready to begin the MRI portion of the study, which consists of two in-magnet assessments and three neurofeedback or sham sessions, all taking place at the Magnetic Resonance Research Center in the Anlyan Center in New Haven, CT. The specific in-magnet procedures are described in more detail in the following sections *i.* – *iv.*

All subjects who take part in MR imaging are screened at each visit, using screening conventions that are standard for magnetic resonance studies, to ensure they do not have any metallic implants, shrapnel, pacemakers, etc. Subject will be screened to make sure they are not under the influence of illicit substances using urine analysis and a breathalyzer. Based on the results of the urine test and breathalyzer, the researchers will determine whether to run the participant through the study protocol that day or to postpone participation to a later date as to avoid a potential dampening of study effectiveness due to intoxication. Women of child-bearing age will only be included if they assure us they are not pregnant. A free urine pregnancy test will be offered to them to use privately if they wish.

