Before each in-magnet assessment, subjects also undergo brief clinical assessments at the Yale Magnetic Resonance Research Center (MRRC). During these sessions, symptoms of PTSD and depression will be collecting using brief self-report checklists. Information regarding any adverse event will also be solicited and recorded.

Subjects will be escorted to and from the scanner by research personnel who will remain present throughout the entire assessment. Before each in-magnet assessment, participants will be required to fill out an MR Safety Questionnaire, endorsing no rule-outs for MR imaging, and walk through a metal detector to ensure they have no ferromagnetic metals on or in their person. The United States Food and Drug Administration (FDA) guidelines for magnet strength and exposure to radio waves will be carefully observed during all scanning sessions. During in-magnet assessments, MR imaging of the brain will record the three dimensional anatomy of the brain, using conventional 3D gradient echo sequence to obtain high-resolution slices of the brain. Images of the subject's brain will also be taken while subjects engage in a specific task (described in more detail in Section III.B.). Thousands of images will be obtained on each subject for each scanning session. This will provide enough information to calculate which regions alter their MRI signal during the activation, or to examine which regions vary in signal level in a correlated manner. We may also collect diffusion tensor imaging (DTI) data which is most commonly used to examine the integrity of white matter tracts. The total imaging time in a single scanning session will not exceed 90 minutes for any subject. During MR scans, components of the Siemens Physiologic Monitoring Unit will be used to take recordings of the subject's pulse (via a pulse-oximeter placed on their finger), respiration (via a pneumatic belt), and galvanic skin response (via sensors on the fingers). This equipment is designed to be completely MR compatible. The records of pulse and respiration will be used during data processing to remove physiologic noise from the images. In order to minimize subject head motion during the MR scans, we may place tape across the subject's forehead or chin. This provides tactile feedback about head motion.

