Over the course of this procedure, subjects will be asked to report various aspects of their experience – this will include responding to questions regarding their perceived control over their brain activity.

- i. In-Magnet Assessment 1: MPRAGE, Resting State, Initial Control Runs, and Localizer. If time allows, DTI data will also be collected.

During the first in-magnet assessment, a high resolution structural image will be collected using an MPRAGE sequence. Functional resting state data will be collected, as well as four control runs. During the resting state sessions spontaneous pupil dilation will be measured using a Eyelink 1000 system. As seen in Figure 2, control runs involve a resting period, exposure to a provocative audio clip, a period of down-regulation where participants try to bring down their amygdala activity, and a final resting period. In order to minimize anticipation and rumination regarding the upcoming or preceding stressor, resting periods are separated from the provocative audio clip and subsequent period of down-regulation by a 1-back memory task (seen in Figure 2 as “1-bk”). These memory tasks provide a cognitively-engaging distraction for the subject, preventing anticipatory and spill-over amygdala activity during resting periods and allowing for a more valid baseline to be established.

Rest	1-bk	Prov audio clip	Down-regulate	1-bk	Rest
60s	30s	60s	60s	30s	60s

Figure 2: Schematic illustration of a control task run. Control assessed based on activity in the target region of the amygdala in the down-regulate blocks (relative to rest)

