After randomization, subjects will undergo a total of 18 NF or sham feedback runs, carried out over three separate sessions one half of a week apart from one another. Each session tends to be composed of 6 NF or sham runs. However, extenuating circumstances (e.g., technical errors, subjects' schedules) may necessitate the 18 NF or sham runs to be spread out over more than three sessions.

In NF runs, an arrow at the top of the screen indicates the subject's current goal. A red arrow pointing upward prompts the subject to listen to the provocative auditory clip and *not* try to control their brain activity pattern. A blue arrow pointing downward prompts the subject to try to decrease activity in the target area. A white arrow pointing to the right indicates a rest period. In all blocks, a color-coded feedback line is presented below the arrow. The line is updated every 2 seconds throughout the scan to indicate activity in their target area. During the red block, a provocative audio clip is playing. Subjects are instructed not to try to control their activity during this period. The provocative auditory stimulus ends when the blue block begins, but subjects often have high activity in this period due to rumination. Their goal is to decrease this activity during the blue period. Before engaging in this task, subjects are given instructions about what to do during each block, and are informed that there is a 6-8 second delay between changes in activity in their target brain area and changes in the line graph due to the slow blood flow response and processing delays.

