The sham feedback is identical to the NF, except for the fact that the feedback line displayed to the subject is taken from the amygdala time-course of a previous subject who received NF, rather than from the current level of amygdala activity of the present subject. This allows the sham subject to get a similar impression of success (or lack thereof) compared to the NF subject they were matched to, without receiving any true neurofeedback. While this does involve a degree of deception (as subjects will believe that the feedback they are receiving is based on their brain activity), subjects in the sham condition will be told at the end of the study that the feedback they received was a control intervention and will be offered the chance to receive the experimental neurofeedback intervention. It is important to note that although the feedback line in the sham condition comes from a past subject, the

audio clips in sham runs will still be based on the sham subject's personal memories, and the onset and offset of provocative sound files is time-locked across subjects.

iv. In-Magnet Assessment 2: Resting State, Post-Intervention Control Runs, DTI (if time allows).

Upon completion of all 18 NF or sham runs, subjects will take part in a second in-magnet assessment where resting state data will again be collected and they will also complete four more control runs. During the resting state sessions spontaneous pupil dilation will be measured. These runs are identical in design to the initial control runs described in Section C.i. These final control runs will allow us to see how much control subjects gain over their amygdalae in the sham versus NF conditions. If time allows, DTI data may also be collected in this session.

v. Follow-Up Scan: Resting State, Long-Term Follow-Up Control Runs, DTI.

One month after the completion of In-Magnet Assessment 2, subjects will take part in an approximately hour-long scan where they will perform additional control task runs and where resting state and DTI data will be collected. During the resting state sessions spontaneous pupil dilation will be measured.

D. Clinical Assessments

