i. *Preprocessing:* Data will be motion corrected using SPM (<http://www.fil.ion.ucl.ac.uk/spm/>) and all subsequent analyses will be done using Yale BiolImage Suite software package.

- ii. *Registration:* The Montreal Neurological Institute (MNI) brain will be used as a reference coordinate system. Functional imaging data for all subjects will be transformed to the space of the MNI brain via a series of registrations (functional → anatomical → MPRAGE → MNI space) that have all been visually inspected.
- iii. *Localizer analyses:* The localizer run (see section I.4. *Research Plan*) will be used to define the target region for NF. First, a whole brain “t-map” will be computed by calculating voxel-wise t-tests contrasting activity during the trauma script exposure period to activity in the resting periods, after adjusting for hemodynamic delay. This is not a true t-map due to autocorrelation, but is useful for identifying the voxels with peak activation in the amygdala. The 30 peak voxels (subject to a cluster filter of 4) falling in the amygdala will be defined as the target area.

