- iv. *Control task activation analyses:* Control over the amygdala target region will be computed by running voxel-wise regression analyses separately for the two categories of traumas – trained (traumas with which the subject engaged in NF) and untrained (traumas that the subject was not exposed to during NF). Four regression analyses will be run per subject – one per category from each of the two assessment sessions. Regressors will be defined for the task periods using boxcar functions convolved with a canonical hemodynamic response function. Three regressors will be used, corresponding to the provocation block, the down-regulate blocks of interest, and the 1-back periods (the lattermost being included to remove the effects of the 1-back periods and make contrasts relative to the rest blocks). Resulting maps of beta values for the regulate and provocation blocks will be transformed to a common space (see above section I.b.) and masked with the target region (also transformed to common space). Average value in the target region will be computed separately from beta maps for the provocation and down-regulate blocks to yield estimates of activation in the amygdala in each condition of each assessment session for the trained and untrained trauma memories. **All analyses outlined in the following sections will use data from the regulation blocks of the untrained traumas unless otherwise noted.**
- v. *Resting state analyses:* In addition to the offline neuroimaging data analyses described above in section I., resting state data collected during each In-Magnet Assessment will be low-pass filtered (0.1 Hz), motion parameters, and the average time-courses of the ventricles and white matter will be regressed from the data. Seed maps of connectivity to the amygdala will then be computed. First, the time-courses of voxels in the target area will be averaged to yield a reference seed region time-course. This time-course will be correlated with the time-course of activity measured at every voxel in the brain to yield a whole-brain map of r-values. The r-values will be transformed to Gaussian variables via Fisher’s transform. The resulting seed region connectivity maps for each In-Magnet Assessment of each subject will be entered into group-level analyses after transformation to common space (see above section ii.).

B. R61 Phase:

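### Does the amygdala-control analysis need a planned NF-versus-sham comparison of breathing, pulse and head motion in the down-regulate blocks?

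*Combined protocol and SAP*

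**What the plan says.** Control over the amygdala is the average beta in the target region for the down-regulate blocks of the untrained traumas, relative to rest (Section I, 13.A.iv and Figure 2). In the model behind it, "Three regressors will be used, corresponding to the provocation block, the down-regulate blocks of interest, and the 1-back periods". That beta feeds the Go decision (13.B.i), the R33 group-by-time test (13.C.i) and the correlation with symptom change (13.C.ii).

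Noise is handled in two other places. Under 13.A.i, "Data will be motion corrected using SPM". Under 4.C MR Imaging, "The records of pulse and respiration will be used during data processing to remove physiologic noise from the images"; the same paragraph lists pulse, respiration and skin response as recorded during scans. The resting-state pipeline (13.A.v) also regresses out motion parameters. The control-task paragraph does not mention doing so.

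The group analyses in 13.B and 13.C cover amygdala activation, symptom scores, resting connectivity and their correlations. None compares the arms on a physiological trace or on motion.

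**The concern.** The two arms receive different learning signals. In the feedback sessions "subjects will have the chance to experiment with their cognitive strategies and receive direct feedback regarding what is more effective" (4.B). For NF subjects that signal is their own. For sham subjects "the feedback line displayed to the subject is taken from the amygdala time-course of a previous subject who received NF" (4.C.iii). A change in breathing that happens to lower the displayed line could therefore be reinforced in NF and not in the same way in sham. Randomization does not protect against a difference that the intervention itself creates.

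If NF subjects carried such a habit into the control runs, part of the measured control could be a vascular or motion effect. It would then enter the Go effect size and the R33 interaction, with no planned table to reveal it. The direction relative to Go cannot be settled from the text: 13.B.i looks for larger activation in NF, while of the feedback task 4.C.iii says "Their goal is to decrease this activity during the blue period". That is a separate wording matter.

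**Working it through.** **Inputs.** From Figure 2: rest 60, 1-back 30, provocation 60, down-regulate 60, 1-back 30, rest 60, so 300 s per run and a down-regulate share of p = 60/300 = 0.2. From 13.A.iv: three convolved boxcar regressors. From Section III, item 1: 60 subjects. Assumed: a double-gamma response function, sampling every 1 to 3 s, one intercept per run, one to three untrained runs per session, and equal arms (4.C.ii says only that NF is never smaller than sham). The plan states no artefact size, SD or power for this point, so there is no figure of its own to reproduce.

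**1. Pass-through with no correction.** Let X hold the intercept and the three regressors, and let s be a unit step in the down-regulate block. The shift in the down-regulate beta is the matching element of (X'X)⁻¹X's. It is 0.90 to 0.92 across the sampling rates, and 1.00 if the nuisance signal has the shape of the haemodynamic response. The three regressors alone do not separate a block-timed signal from control.

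**2. Pass-through with the step promised in 4.C.** The method of that step is not described, so take one simple form: a recorded trace equal to k·s plus unit white noise is regressed out before the model is fitted. The share of the step that remains is 1/(1 + k²p(1−p)), with p(1−p) = 0.2 × 0.8 = 0.16.

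| k | remaining share | × 0.90 to 0.92 |
|---|---|---|
| 1 | 1/1.16 = 0.862 | 0.78 to 0.79 |
| 2 | 1/1.64 = 0.610 | 0.55 to 0.56 |
| 4 | 1/3.56 = 0.281 | 0.25 to 0.26 |

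Entering the trace in the same model as the task regressors would remove less, because those regressors already claim most of the block-timed variance. The residual contamination therefore depends on a step that is planned but not detailed, and the uncorrected figure is an upper range.

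**3. Adding motion parameters.** Six motion terms per run, simulated independently of the block, leave 0.90 to 0.92 of the step if they are white noise and a median of 0.75 to 0.81 if they drift slowly. The standard error rises by 1% to 3% in the first case and about 1.9 times in the second (at fixed residual variance). If within-subject error is a share w of the between-subject variance, the SD grows by √(1 − w + w·1.9²):

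- w = 0.1: 1.12, so d = 1.0 becomes 0.89
- w = 0.5: 1.52, so d = 1.0 becomes 0.66
- w = 0.9: 1.83, so d = 1.0 becomes 0.55

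Such a model need not expose the artefact, and it can lower d when no artefact is present.

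**4. Precision of a by-arm comparison.** The 95% half-width in SD units is t(0.975, 2n−2)·√(2/n):

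- n = 30: 2.002 × 0.258 = 0.52
- n = 20: 2.024 × 0.316 = 0.64
- n = 10: 2.101 × 0.447 = 0.94

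With 30 per arm the difference detectable at 80% power, two-sided 0.05, is (1.96 + 0.84) × 0.258 = 0.72 SD. The comparison could show a moderate or large difference; it could not establish balance.

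**5. What a difference would mean.** 13.C.ii expects arousal reactivity to be among the symptoms most closely tied to successful amygdala regulation. If NF works as hypothesised, breathing and pulse may well be calmer in the down-regulate block. An arm difference would then accompany success as readily as artefact. A rule that the control result cannot be separated from such a difference would declare a real success uninterpretable.

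**6. Reach.** The symptom correlation in 13.C.ii is computed across NF subjects only. An NF-versus-sham comparison says nothing about what drives it.

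**The case for a change.** The best case for a change is that the beta is the trial's mechanism outcome, that the arms can diverge by design, and that the material is already in hand: pulse and respiration are recorded, and motion parameters are used in 13.A.v. A few sentences and some code would suffice, the primary estimate would not move, and a check set out before results by arm are seen carries more weight than one chosen afterwards. Noise removal, even if complete, does not report whether the arms differed.

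Much of this stands. The omission is real, 13.A.iv does not say how or where the 4.C correction is applied to the control runs, and a reader of a positive result will ask about breathing.

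What it does not show is that a planned rule or result is wrong. The three regressors are introduced as task regressors, which does not rule out the noise handling stated elsewhere. No artefact is documented or sized. Neither proposed output settles the question: a difference in the traces is ambiguous, and the adjusted model is neither sensitive to block-timed signal nor neutral when there is none.

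**Conclusion.** No change to the plan is called for. This is a gap in description that analysts can fill sensibly. The commitment to remove physiologic noise already stands in 4.C, and the traces can be summarised by arm as supporting description without touching any planned test.

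The possible size is bounded only in relative terms: 0.90 to 0.92 of a block-timed step without correction, and about 0.8 to 0.25 under one assumed form of the planned correction for k from 1 to 4. The absolute size cannot be derived from the documents. These figures rest on the Figure 2 timing, a double-gamma response, 1 to 3 s sampling and, for the confidence half-widths, equal arms with between 10 and 30 subjects each. The conclusion would be different if the documents reported a block-timed breathing, pulse or motion difference between NF and sham, or if the 4.C correction were dropped for the control runs. Neither is the case.
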